#### 3.1.7.1 Dose Evaluation Phase

Each subject enrolled in the dose evaluation cohorts of the study will be evaluated for dose-limiting toxicities (DLTs), as defined in Section 3.1.9. Dose de-escalation and evaluation of RCD will be performed based on the available dose levels (see table below) and the respective rules for a standard 3 + 3 study design (see Schema below).

For Arm A, the RCD of BI 1361849 + durvalumab is determined. The starting dose of durvalumab is 1500 mg with possible de-escalation to 750 mg; the dose for BI 1361849 remains constant. For Arm B, the RCD of BI 1361849 + durvalumab from Arm A with the addition of tremelimumab 75 mg is evaluated. There is no dose escalation/de-escalation for Arm B; if there is unacceptable toxicity in Arm B, the arm will be discontinued.

Dose Level Table for Evaluation Phase						
Dose Level	Arm A		Dose Level	Arm B*		
	BI 1361849	Durvalumab		BI 1361849	Durvalumab	Tremelimumab
-1	12 x 80 µg**	750 mg				
Starting	12 x 80 µg**	1500 mg	Starting	12 x 80 µg**	RCD from Arm A	75 mg

[figure not shown]
\*If there is unacceptable toxicity in Arm B, dosing will continue at RCD from Arm A, without tremelimumab.

\*\*BI 1361849 is a vaccine comprising six drug product components (F2408, F2409, F2410, F2624, F2625, and F2626), which are provided and administered separately; each component is administered twice, thus there are 12 administrations of 100 µL (80 µg) each.

**NOTE 1:** The Pharmajet Tropis® device will be used for the administration of the BI 1361849 components. Allowing for a filling volume of 100 µL (80 µg) and 2 administrations per component, the recommended dose per each of the 6 antigen components will be 160 µg (2 x 80 µg), for a total of 960 µg (12 administrations). See Section 6.3.3 for details on the administration of BI 1361849.

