**Figure 2. Dose Escalation and De-Escalation Schema**

Per Figure 2, the RCD for Arm A and Arm B is defined as the highest dose level at which no more than 1 of 6 subjects (i.e., < 33%) experience DLTs. The RCD cannot be determined if none of the predefined dose level cohorts fulfill that criterion. In such case, the arm will be discontinued without an expansion phase.

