### 3.1.9 DLT and MTD/RCD for the Combination Therapy

MTDs will not be determined in this study. Instead, RCDs will be determined in the context of the predefined dose levels used during the dose evaluation phase as per Section 3.1.7.1.

DLTs will be observed over a period of the first 2 cycles of the combination therapy, including the pre-dose assessment for Cycle 3, defined as the **DLT Evaluation Period**. The decisions for dose evaluations, de-escalations and RCD, as described in Section 3.1.7.1 will primarily be based on the number of subjects with DLTs occurring during the DLT Evaluation Period. DLTs occurring outside the DLT Evaluation Period will also be evaluated and may impact such decisions.

DLTs are defined as any adverse events that are possibly, probably, or definitely related to the administration of durvalumab, tremelimumab, or BI 1361849 components, and fulfill any of the following criteria:

1. Any Grade  $\geq 3$  colitis, pneumonitis, neurological event or uveitis.
2. Any Grade 2 pneumonitis, neurological event or uveitis, with the following exception:
  - Grade 2 pneumonitis, neurological event or uveitis that downgrade to Grade  $\leq 1$  within 3 days after onset, whereby maximal supportive care, including systemic corticosteroids, is permitted.
3. Any *other* Grade  $\geq 3$  toxicity, with the following exceptions:
  - Grade 3 irAEs that downgrade to Grade  $\leq 2$  within 3 days, or to Grade  $\leq 1$  or baseline within 14 days after onset, whereby maximal supportive care, including systemic corticosteroids, is permitted.
  - Grade 3 endocrinopathy that becomes asymptomatic when managed with or without systemic corticosteroid therapy and/or hormone replacement therapy.
  - Grade 3 inflammatory reaction attributed to a local antitumor response (e.g., inflammatory reaction at sites of metastatic disease, lymph nodes, etc.).
  - Grade 3 fatigue for  $\leq 7$  days.
  - Grade 3 infusion-related reaction (first occurrence and in the absence of steroid prophylaxis) that resolves within 6 hours with appropriate clinical management.
  - Liver transaminase elevation  $\leq 8$  times ULN that downgrades to Grade  $\leq 2$  ( $\leq 5$  times ULN) within 7 days after onset, whereby maximal supportive care, including systemic corticosteroids, is permitted.

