  - Total bilirubin  $\leq 5$  times ULN that downgrades to Grade  $\leq 2$  ( $\leq 3$  times ULN) within 7 days after onset, whereby maximal supportive care, including systemic corticosteroids, is permitted.
  - Grade  $\geq 3$  neutropenia that (1) is not associated with fever or systemic infection, (2) does not require medical intervention, and (3) improves to Grade 2 within 7 days.
  - Grade 3 and 4 lymphopenia.
  - Grade 3 thrombocytopenia that (1) is not associated with clinically significant bleeding, (2) does not require medical intervention, and (3) improves to Grade 2 within 7 days.
  - Isolated Grade 3 electrolyte abnormalities that are not associated with clinical signs or symptoms and are reversed with appropriate maximal medical intervention within 3 days.
  - Any pre-existing laboratory abnormality that deteriorates to Grade 3/4, but where the increment of deterioration is considered not clinically significant by both investigator and sponsor.
  - Grade 3 or 4 asymptomatic increases in amylase or lipase levels for which appropriate evaluation shows no clinical evidence of pancreatitis.

Immune-related AEs (irAEs) are defined as AEs of immune nature (i.e., inflammatory) in the absence of a clear alternative etiology. In the absence of clinical abnormality, repeat laboratory testing will be conducted to confirm significant laboratory findings prior to designation as a DLT.

While rules for adjudicating DLTs are specified above, an AE that is Grade < 3 or listed as exempt above may also be defined as DLT after consultation with the sponsor and Investigators, based on the emerging safety profiles of durvalumab, tremelimumab, and BI 1361849. Likewise, subjects who become not evaluable for DLT, because they discontinued or interrupted treatment due to toxicities other than DLTs, may be counted as DLT subjects, if the toxicities cannot be managed in accordance with the dosing modifications described in Section 3.1.8.

Subjects who experience a DLT will be discontinued from study treatment and will enter the On Study and Post Study Follow-up (see Section 3.1.16). However, if it is in the best interest of the subject, the Investigator, subject and Sponsor may agree to continue treatment with BI 1361849.

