- In general, hold M and T until resolution to  $\leq$  Grade 1 and after the end of any steroid taper, and discontinue M and T permanently if such resolution does not occur within 60 days (30 days for neurotoxicities). Criteria for temporary hold or permanent discontinuation of M and T may differ by event as detailed below.
- For *myositis/polymyositis*, hold M and T until resolution to  $\leq$  Grade 1; permanently discontinue M and T if it does not resolve to  $\leq$  Grade 1 within 30 days or if there are signs of respiratory insufficiency.
- For *pneumonitis/interstitial lung disease and myocarditis*, the decision to reinitiate M and T upon resolution shall be based upon treating physician's clinical judgment (as long as the event does not meet DLT criteria).
- For *peripheral neuromotor syndromes*, such as *Guillain-Barre* and *Myasthenia Gravis*, follow general instructions above, but always discontinue M and T permanently if there are signs of respiratory insufficiency or autonomic instability.
- For *endocrinopathies, other than isolated hypothyroidism and isolated Type 1 diabetes mellitus*, follow general instructions above, but subjects may be retreated if the endocrinopathy is controlled and the subject is clinically stable while requiring steroid doses of  $\leq$  10 mg/day prednisone equivalent.
- For *isolated hypothyroidism* managed with hormone replacement therapy, *isolated Type 1 diabetes mellitus* treated with appropriate diabetic therapy, and for *sensory neuropathy/neuropathic pain*, holding M and T is at the discretion of the Investigator.
- For *elevated creatinine* or *rash*, M and T should be held until resolution to  $\leq$  Grade 1 or baseline and after completion of steroid taper.
- For *vitiligo*, no dose modification required.

## Grade 3

- In general, hold M and T until resolution to  $\leq$  Grade 1, and after the end of any steroid taper, and discontinue M and T permanently if such resolution does not occur within 60 days (30 days for neurotoxicities and rash). Criteria for permanent discontinuation of M and T may differ by event as detailed below.
- For *myositis/polymyositis*, follow Grade 2 instructions above.
- For *peripheral neuromotor syndromes* (such as *Guillain-Barre* and *Myasthenia Gravis*), apply respective Grade 2 rules.
- For *endocrinopathies*, follow Grade 2 instructions above.
- For *diarrhea/colitis*, permanently discontinue M and T if toxicity does not improve to  $\leq$  Grade 1 within 14 days.

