- For *pneumonitis/interstitial lung disease, myocarditis, and elevated serum creatinine (e.g., nephritis or renal dysfunction)*, always discontinue M and T permanently.
- For *asymptomatic increases of amylase or lipase* levels, hold M and T, and if complete work up shows no evidence of pancreatitis, M and T may be continued.
- For *hepatitis*, discontinue M and T permanently for (1) transaminases or bilirubin not resolving to  $\leq$  Grade 1 or baseline within 14 days, (2) transaminases  $> 8 \times$  the upper limit of normal (ULN) or bilirubin  $> 5 \times$  ULN, or (3) any case meeting Hy's law criteria (as defined in FDA Guidance Document "Drug-Induced Liver Injury").
- For *rash*, M and T should be held until resolution to  $\leq$  Grade 1 or baseline.

CONFIDENTIAL

MEDI4736 (M) and Tremelimumab (T) Dose Modification Due to Toxicity

Grade 4
 
 
• In general, discontinue M and T permanently.
 
• For endocrinopathies, follow Grade 2 instructions above.
 
• For asymptomatic increases of amylase or lipase levels, hold M and T, and if complete work up shows no evidence of pancreatitis, M and T may be continued.
 

Infusion-related Reactions
 
Grade 1
 
 
• The infusion rate of M and T may be decreased 50% or temporarily interrupted until resolution of the event.
 
• Acetaminophen and/or antihistamines may be administered per institutional standards at the discretion of the Investigator.
 
• Premedication for subsequent doses should be considered.
 
• Steroids should not be used for routine premedication of <math>\leq</math>Grade 2 infusion reactions
 
 
Grade 2:
 
 
• Same as Grade 1, but consider giving subsequent infusions at 50% of the initial infusion rate.
 
 
Grade 3 and 4:
 
 
• The infusion must be stopped immediately and treatment permanently discontinued.
 
• Manage severe infusion-related reactions per institutional standards (e.g., IM epinephrine, followed by IV diphenhydramine and ranitidine, and IV glucocorticoid).
 

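### A related Grade 3 immune myocarditis that recovers in time is by default not a DLT, although the dosing rules always end both antibodies for it

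*Protocol*

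**What the plan says.** **DLT definition (Protocol 3.1.9).** Criterion 1 makes related colitis, pneumonitis, neurological events and uveitis DLTs at Grade 3 or higher, with no recovery window. Every other related Grade 3 or higher toxicity falls under criterion 3. The first exception there releases a Grade 3 immune-related event that drops to Grade 2 or lower within 3 days, or to Grade 1 or lower "or baseline within 14 days after onset, whereby maximal supportive care, including systemic corticosteroids, is permitted". Myocarditis is named nowhere in 3.1.9.

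**Dosing rules (Protocol 8.3.1, immune-related events, Grade 3).** One bullet covers pneumonitis/interstitial lung disease, "myocarditis, and elevated serum creatinine (e.g., nephritis or renal dysfunction"). For all of these, durvalumab and tremelimumab are always stopped for good, with no recovery condition.

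**Discretion (Protocol 3.1.9).** An event that is exempt or below Grade 3 "may also be defined as DLT after consultation with the sponsor and Investigators". Subjects who become non-evaluable through other toxicity "may be counted as DLT subjects, if the toxicities cannot be managed in accordance with the dosing modifications described in Section 3.1.8".

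**Decision rule (Protocol 3.1.7.1).** The text that accompanies the Figure 2 schema states that "the RCD for Arm A and Arm B is defined as the highest dose level at which no more than 1 of 6 subjects" have a DLT. For the triple combination: "There is no dose escalation/de-escalation for Arm B; if there is unacceptable toxicity in Arm B, the arm will be discontinued".

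**The concern.** The RCD is a primary endpoint of the dose evaluation phase, and 3.1.9 says that decisions rest primarily on the number of subjects with DLTs. A Grade 3 myocarditis that settles on steroids within two weeks ends both antibodies in that subject, yet by default adds nothing to that number. Pneumonitis, in the same 8.3.1 bullet, is always counted at Grade 3. With one other DLT in the cohort, the difference is 2 of 6 (fails) against 1 of 6 (passes).

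**Working it through.** **1. The two sections side by side, related immune events at Grade 3**

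| Event | 3.1.9 | 8.3.1 (durvalumab, tremelimumab) |
|---|---|---|
| Pneumonitis | Always a DLT | Always stop |
| Myocarditis | Not a DLT if recovered in 3 or 14 days | Always stop |
| Creatinine/nephritis | Not a DLT if recovered in 3 or 14 days | Always stop |
| Colitis | Always a DLT | Stop only if not Grade 1 or lower within 14 days |

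Grade 4 myocarditis, and Grade 3 myocarditis that misses both windows, remain DLTs.

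**2. What happens to the subject.** Section 4.1.2 requires a subject without a DLT to have at least 75% of the scheduled antibody doses and at least 4 of 5 vaccinations in the first two cycles. Each antibody has two doses in that period.

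- Event in Cycle 1: 1/2 = 50% in Arm A and 2/4 = 50% in Arm B. The subject is non-evaluable, and 3.1.11 says such subjects are replaced.
- Event after Cycle 2 Day 1: 100% of the antibody doses. The schedule places four vaccinations by that day (Cycle 1 Days 1, 8 and 15, Cycle 2 Day 1), so the subject can be an evaluable non-DLT.

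**3. The plan's rule.** 1/6 = 16.7%, below the stated 33%. 2/6 = 33.3%, not below it. The rule is consistent.

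**4. Expected effect at one dose level.** The documents give no event rates, so these are assumptions: p is the total dose-limiting rate including the event, and e is the rate of recovering Grade 3 myocarditis (0.5% or 1%). The chance of passing at rate r is P(X ≤ 1), X ~ Bin(6, r), which equals (1−r)^5 (1+5r). Use r = p if the event is counted, p−e if it is exempt and scored as a non-DLT, and (p−e)/(1−e) if the subject is replaced. Example, p = 0.10: 0.9^5 × 1.5 = 0.8857.

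| p | e | Counted | Exempt | Replaced | Shift (points): exempt, replaced |
|---|---|---|---|---|---|
| 10% | 0.5% | 0.8857 | 0.8954 | 0.8945 | 1.0, 0.9 |
| 10% | 1% | 0.8857 | 0.9048 | 0.9032 | 1.9, 1.7 |
| 20% | 0.5% | 0.6554 | 0.6676 | 0.6652 | 1.2, 1.0 |
| 20% | 1% | 0.6554 | 0.6799 | 0.6752 | 2.5, 2.0 |
| 33% | 0.5% | 0.3578 | 0.3678 | 0.3645 | 1.0, 0.7 |
| 33% | 1% | 0.3578 | 0.3780 | 0.3714 | 2.0, 1.4 |

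The chance of at least one such event in six is 1−(1−e)^6 = 0.030 or 0.059.

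**5. Effect if one such event occurs.** With DLT rate q in the others, the level passes with probability P(0 of 5) if the event is counted, P(≤1 of 5) if exempt and P(≤1 of 6) if replaced.

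| q | Counted | Exempt | Replaced |
|---|---|---|---|
| 10% | 0.590 | 0.919 | 0.886 |
| 20% | 0.328 | 0.737 | 0.655 |
| 33% | 0.135 | 0.468 | 0.358 |

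**6. Arm A.** The figures in steps 4 and 5 are per dose level. Arm A can fall back to 750 mg. If the rate is 10% at both levels (an assumption), the chance of no RCD at all is 0.114² = 0.013 if counted and 0.095² to 0.105² = 0.009 to 0.011 if exempt.

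**The case against.** The two sections serve different purposes: 8.3.1 governs one subject's further dosing, and 3.1.9 governs a cohort decision. Nowhere does the protocol say that a permanent stop must be a DLT. A reader might infer that the sections contradict each other, or that every mandated stop belongs in the count. The documents do not support that, because the lists differ in both directions. Colitis is stricter in 3.1.9. A first Grade 3 infusion reaction that resolves within 6 hours is expressly exempt although 8.3.1 ends treatment. Bullous rash of any grade ends treatment but is not a listed DLT at Grade 1 or 2, and the liver-test limits differ too. For that reason automatic counting of recovered creatinine/nephritis is not argued here.

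A reader might also take the omission for a proven oversight. The version history shows that Amendment 2 added myocarditis to the pneumonitis bullet of 8.3.1 on FDA recommendation, with no matching change to 3.1.9 recorded, and that Amendment 3 aligned 3.1.9 with 8.3.1 for amylase and lipase. That is suggestive, not proof.

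The discretionary clauses, the safety panel's cohort reviews (3.1.14) and the SAP tables of discontinuations (9.1.1) are real mitigation, and individual safety is covered because the drugs stop. But both clauses are permissive. The second reaches only non-evaluable subjects, and it is doubtful even there: 3.1.8 refers to 8.3, where the permanent stop is itself the prescribed management. The SAP tables belong to the final analysis, not to the RCD decision. SAP sections 2.2 and 4.3 add no DLT rule that settles the point.

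Finally, the Grade 2 bullet of 8.3.1 says that restarting "shall be based upon treating physician's clinical judgment (as long as the event does not meet DLT criteria"), while criterion 2 reads "Any Grade 2 pneumonitis, neurological event or uveitis, with the following exception" and does not name myocarditis. A reader might see an open route to re-treatment. It is mainly a wording point: 8.3.1 permanently ends both antibodies for biopsy-proven immune-mediated myocarditis of any grade, the same bullet also covers pneumonitis, where criterion 2 does apply, and adjudication can reach the rest.

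**Conclusion.** The point holds for Grade 3 myocarditis and is minor. By default, a related case that recovers in time is left out of the DLT count, although it always ends both antibodies; only discretion brings it in. The expected shift is 0.7 to 2.5 points in the chance that a dose level passes. A large distortion of the RCD is not a fair inference: the wide contrasts in step 5 apply only once such an event has occurred and only if nobody adjudicates it as a DLT. Protocol 7.1.8 calls myocarditis rare but gives no rate.

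The figures rest on the assumed rates, on independent subjects, and on the stated 1-of-6 rule (the Figure 2 schema is not visible in the text available). They describe Arm B directly and overstate the effect on whether Arm A obtains any RCD.

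**What to change.** 1. Either name myocarditis with pneumonitis in criterion 1 of 3.1.9 (Grade 3 or higher), or add to the first exception of criterion 3: *This exception does not apply to Grade 3 myocarditis.* Naming the event leaves the infusion-reaction exemption untouched.
2. At each RCD review, list all permanent stops that 8.3.1 mandated in the DLT Evaluation Period, including nephritis/creatinine, beside the DLT count, so that the panel can adjudicate them under the existing clauses. If dose evaluation is already complete, the list can still go into the study report.
3. Leave automatic counting of recovered Grade 3 creatinine/nephritis to the sponsor. Tidying the Grade 2 myocarditis wording is optional.

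The cost is one small edit to 3.1.9, one line in the cohort review and a slightly higher DLT count. At an acceptable 10% total rate, counting the event raises the chance that a dose level fails from 0.095–0.105 (exempt) or 0.097–0.106 (replaced) to 0.114. This matters most in Arm B, where failure ends the arm. If one such event occurs and the others have a 10% rate, the chance of passing is 0.59, against 0.92 if exempt or 0.89 if replaced. The sponsor should accept that trade-off knowingly.

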### 3.1.10 Subject Withdrawal from Treatment or from Study

A subject will be **withdrawn from study treatment** for any of the following reasons:

1. Withdrawal of consent for further treatment
2. Pregnancy or intent to become pregnant
3. DLT at any time (see Section 3.1.9)
4. Progressive disease requiring alternative systemic treatment
5. Significant protocol violation or noncompliance that, in the opinion of the Investigator or Sponsor, warrants withdrawal
6. Development of intercurrent, non-cancer-related illnesses or complications that prevent either continuation of therapy or regular follow-up
7. Best medical interest of the subject (at the discretion of the Investigator)

Discontinuation from receiving study treatment does not mean that the subject is withdrawn from the study. If applicable, subjects who are withdrawn from study treatment should undergo the planned On Study Follow-up procedures (see Study Flowchart, Section 3.2), followed by the Post Study follow-up period (see Section 3.1.16).

A subject will be **withdrawn from the study** for the following reasons:

1. Best medical interest of the subject at the discretion of the Investigator
2. Initiation of alternative anticancer therapy (marketed or investigational)
3. Withdrawal of consent for all follow-up
4. Lost to follow-up
5. Death

Section 7.2.6 provides additional details regarding documentation for early subject withdrawal from study treatment and early withdrawal from study.

See also Sections 8.3 and 8.4 for subject withdrawal from treatment due to necessary dosing interruptions or discontinuations.

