### 3.1.8 Dosing Adjustments, Delays, and Discontinuations

Individual subject dosing adjustments due to toxicity will be allowed/may be required in accordance with the “Dose Adjustment and Management Guidelines” for toxicity related to durvalumab / tremelimumab and BI 1361849, outlined in Section 8.3 and Section 8.4, respectively.

If a toxicity occurs that requires toxicity management in accordance with Sections 8.3 or 8.4, and the toxicity causing drug can be clearly identified, then the respective guideline should be followed. If the toxicity causing drug cannot be identified, then the more conservative guideline should be followed.

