**7.1.8 Adverse Events of Special Interest (AESIs)**

An adverse event of special interest (AESI) is one of scientific and medical interest specific to the understanding of the investigational products and may require close monitoring and rapid communication by the Investigator to the Sponsor. An AESI may be serious or non-serious. The rapid recording of all AEs, including AESIs, allows ongoing surveillance of these events in order to characterize and understand them in association with the use of the investigational products.

AESIs for durvalumab and tremelimumab include but are not limited to events with a potential inflammatory or immune-mediated mechanism and which may require more frequent monitoring and/or interventions such as steroids, immunosuppressants and/or hormone replacement therapy. These AESIs are being closely monitored in clinical studies with durvalumab monotherapy and combination therapy. An immune-related adverse event (irAE) is defined as an adverse event that is associated with drug exposure and is consistent with an immune-mediated mechanism of action and where there is no clear alternate aetiology.

Serologic, immunologic, and histologic (biopsy) data, as appropriate, should be used to support an irAE diagnosis. Appropriate efforts should be made to rule out neoplastic, infectious, metabolic, toxin, or other etiologic causes of the irAE.

If the Investigator has any questions in regards to an AE being an irAE, the Investigator should promptly contact the Medical Monitor.

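### Protocol 8.3.1 lets durvalumab and tremelimumab resume after some events that 3.1.9 makes DLTs and for which 3.1.10 requires a stop; only one of its bullets defers to DLT status

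*Protocol*

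**What the plan says.** **The stop.** Protocol 3.1.10 gives "DLT at any time (see Section 3.1.9" as the third reason for withdrawal from study treatment, and SAP 5.0 carries the same reason into the disposition table. Protocol 3.1.9 says "Subjects who experience a DLT will be discontinued from study treatment". Its only exception is that BI 1361849 may continue if investigator, subject and sponsor agree. Durvalumab and tremelimumab have none.

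**What counts as a DLT.** Only events at least possibly related to a study drug can count. Under 3.1.9:
- Criterion 1 takes any Grade ≥3 "colitis, pneumonitis, neurological event or uveitis", with no exception for recovery.
- Criterion 2 takes the Grade 2 forms of the last three. The exception, which begins "Grade 2 pneumonitis, neurological event or uveitis that downgrade to Grade", requires a fall to Grade ≤1 within 3 days.
- Criterion 3 takes other Grade ≥3 toxicities, with listed exceptions. One covers Grade 3 immune-related events (irAEs) that reach Grade ≤2 within 3 days, or Grade ≤1 or baseline within 14. Another is "Grade 3 endocrinopathy that becomes asymptomatic when managed with or without systemic corticosteroid therapy", which is limited to Grade 3.

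**The table.** For Grade 2 and 3 irAEs, 8.3.1 generally holds both antibodies and makes the stop permanent only if the event has not resolved within 60 days. The limit is 30 days for neurotoxicity, myositis and Grade 3 rash, and 14 days for Grade 3 diarrhea/colitis. For Grade 2 sensory neuropathy even the hold is optional. Grade 4 endocrinopathy is sent to the Grade 2 instructions, which permit retreatment once it is controlled. DLT status is mentioned once in 8.3.1, in the Grade 2 pneumonitis/ILD and myocarditis bullet, and nowhere in 8.4.

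**The concern.** For the same event, one section requires both antibodies to stop and another sets out when they may be given again. Because a single bullet in 8.3.1 yields to DLT status, a reader may infer that the other bullets do not. A site that manages toxicity from the table could therefore re-dose a subject after an event for which 3.1.10 requires withdrawal. Some of these events are serious: 3.1.14 names symptomatic treatment-related Grade ≥3 neurological toxicity and uveitis among those that may lead to suspension of the study.

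There is a smaller analysis consequence. Stopping or resuming changes exposure and decides whether the subject appears under the DLT reason in SAP 5.0. It also decides whether PFS is censored at that discontinuation, because Protocol 4.2.1.4 and SAP 7.4 censor subjects who stop treatment for reasons other than progression or death. The documents do not allow that effect to be sized.

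**Working it through.** The plan gives no figure to reproduce, so the check sets the sections side by side. The inputs are the DLT criteria (3.1.9), the resumption limits (8.3.1) and the recovery limit in 8.4 (4 weeks, 28 days, Grade ≥3 only). The 8.4 limit matters because 3.1.8 says "If the toxicity causing drug cannot be identified, then the more conservative guideline should be followed".

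Overlap in days = last day on which recovery still permits re-dosing, minus last day on which recovery would have kept the event from being a DLT (0 where 3.1.9 has no recovery exception).

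| Related event | Becomes a DLT (3.1.9) | Re-dosing allowed if resolved by (8.3.1) | Overlap, cause is durvalumab/tremelimumab | Overlap, cause unknown (stricter of 8.3 and 8.4) |
|---|---|---|---|---|
| Grade 3 colitis | at onset | day 14 | 14 − 0 = 14 | 14 (8.3.1 already stricter) |
| Grade 3 neurological | at onset | day 30 | 30 − 0 = 30 | 28 − 0 = 28 |
| Grade 3 uveitis | at onset | day 60 | 60 − 0 = 60 | 28 − 0 = 28 |
| Grade 2 neurological | not Grade ≤1 by day 3 | day 30 | 30 − 3 = 27 | 27 |
| Grade 2 uveitis | not Grade ≤1 by day 3 | day 60 | 60 − 3 = 57 | 57 |
| Grade 3 rash, myositis | not Grade ≤2 by day 3, nor Grade ≤1 or baseline by day 14 | day 30 | 30 − 14 = 16 | 28 − 14 = 14 |
| Other Grade 3 irAE with no rule of its own | as above | day 60 | 60 − 14 = 46 | 28 − 14 = 14 |

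Uveitis is not named in 8.3.1 and falls under the general irAE rule. Controlled Grade 4 endocrinopathy also overlaps, because the 3.1.9 exception stops at Grade 3, but the table says only that such subjects may be retreated, so no window is counted.

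Three limits apply.

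1. 8.3.1 already requires a permanent stop for peripheral neuromotor syndromes with respiratory insufficiency or autonomic instability, and for myositis with respiratory insufficiency. Where the cause is unknown, 8.4 also stops events that are potentially life-threatening or disabling. The windows exclude these.
2. The Grade 3 bullet covers diarrhea as well as colitis. Immune-related diarrhea without colitis falls under criterion 3, whose 14-day exception matches the 14 days in 8.3.1. Only colitis conflicts.
3. The rule for other (non-immune) Grade 3 events allows resumption on improvement to Grade ≤2 within 7 days, or to Grade ≤1 or baseline within 14. It meets the DLT definition only for related events with no listed exception. It also serves events judged unlikely to be related, which are never DLTs, so it is secondary.

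No conflict was found for hepatitis, Grade 3 pneumonitis, myocarditis, raised creatinine, infusion reactions or asymptomatic amylase/lipase rises.

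The requirement that a DLT be drug-related removes little from the table, since 7.1.8 says "An immune-related adverse event (irAE) is defined as an adverse event that is associated with drug exposure".

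**The case against.** The best defence is that precedence can be read from the text. The withdrawal language in 3.1.9 and 3.1.10 is mandatory. 3.1.9 speaks of non-DLT toxicities being counted as DLTs "if the toxicities cannot be managed in accordance with the dosing modifications described in Section 3.1.8", which implies that the modification rules are meant for events that are not DLTs. The closing reference in 3.1.10 to 8.3 and 8.4 adds grounds for withdrawal and removes none. Most 8.3.1 limits are outer bounds, so a site that stops complies with both sections. All of this stands as evidence of intent. It does not make the table say so, and the single caveat points the other way. The sponsor has aligned these sections before: the version history (8.1) records that Amendment 3 added the amylase/lipase exception to 3.1.9 to match 8.3.1.

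The rule to follow the more conservative guideline does not settle the matter. It chooses between 8.3 and 8.4 when the causative drug is unknown, not between either of them and the DLT stop, and the last column of the table shows that windows remain.

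It is also fair that the worst events may reach the sponsor or the safety panel before any re-dosing (3.1.14, 7.1.8). The separate MedImmune toxicity guideline cited in 8.3.1 is not available here, and its treatment of DLTs is unknown.

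Stronger readings are tempting but unsupported. A reader might infer that the whole diarrhea/colitis bullet is void, or that the table permits re-dosing after respiratory compromise; the limits under the working rule out both. A reader might take the day counts as a measure of risk, or the planned expansion share at the RCD (14 of 20 per arm) as the proportion affected. The documents give no rate for these events, so neither follows.

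**Conclusion.** The inconsistency is real and should be corrected, though it is narrower than a general clash between the DLT rule and the toxicity table. It concerns related Grade 3 colitis, Grade 2 and 3 neurological events and uveitis, late-resolving Grade 3 irAEs and, in permissive wording, controlled Grade 4 endocrinopathy. The overlap is 14 to 60 days when the cause is identified as durvalumab or tremelimumab. When it is unknown, the Grade 3 windows shrink to between 14 and 28 days and the Grade 2 windows stay at 27 and 57. These figures take the limits as running from onset and 4 weeks as 28 days.

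The DLT stop is probably meant to govern; the defect is that 8.3.1 says so in one place only. A reader might infer that dose finding is compromised. It is not: an event that meets 3.1.9 counts as a DLT whether or not the subject is later re-dosed, so DLT counts and the RCD do not change. No number of affected subjects is claimed.

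**What to change.** At the head of the 8.3.1 table, state: *The hold-and-resume rules below apply only to events that do not meet the Section 3.1.9 DLT criteria; once an event meets them, at onset or later, durvalumab and tremelimumab are permanently discontinued per 3.1.9/3.1.10.* Add a cross-reference in 8.4 that keeps the allowance to continue BI 1361849 by agreement.

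Optionally, confirm in 3.1.10 that the DLT reason covers expansion subjects. Protocol 3.1.7.1 and SAP 2.2 tie DLT evaluation to the dose evaluation cohorts, but 3.1.10 and SAP 5.0 set no phase limit on withdrawal, so this is a clarification only.

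The cost is one sentence and one cross-reference, with no new procedures. The downside is that some subjects whose toxicity has resolved would not be re-dosed. If the sponsor would rather let 8.3.1 govern for particular events, 3.1.10 should say so.
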